3.0 Protocol Synopsis

Sponsor/Company	Zimmer Knee Creations, Inc.
Study Title	A Longitudinal Outcomes Study of the Subchondroplasty [®] Procedure in the Foot/Ankle
Protocol Number	KC.CR.IAM.16.2
Implant Material	AccuFill [®] Bone Substitute Material
Treatment	Injection of a flowable calcium phosphate (CaP) synthetic bone-void filler into osseous defects in the bones of the Foot and/or Ankle (Subchondroplasty Procedure (SCP [®])) as demonstrated by bone marrow lesions on diagnostic imaging.
Number of Study Sites	Up to 25 study sites
Study Population	Approximately 250 subjects, each with at least one bone marrow lesion (BML) in any of the bones of the foot and/or ankle who have elected to undergo or who have undergone the Subchondroplasty procedure, will be enrolled in the study.
Study Design	A post-market, multi-center, longitudinal, patient-reported outcomes study of a commercially available AccuFill bone substitute material used in the Subchondroplasty procedure of the foot and/or ankle.
Study Objectives	To collect data on the short- and long-term outcomes for subjects who are undergoing or who have undergone the Subchondroplasty procedure in the foot and/or ankle in a standard clinical setting. Outcomes to be assessed include medication usage, pain, function, health status and patient satisfaction.
Inclusion/Exclusion Criteria	
Candidates must meet ALL of the following:
 
 1) Subject has at least one bone defect such as a BML, cyst or stress fracture confirmed by diagnostic imaging. 2) Surgeon considers the patient appropriate for the SCP procedure. 3) Subject provides voluntary signature on the IRB-approved Informed Consent. 4) Subject is at least 18 years of age. 5) Subject must be physically and mentally willing and able, in the Investigator's opinion at the time of enrollment, to complete outcome forms via the internet, telephone, or regular mail. 
Candidates will be excluded if they meet ANY of the following:

A Longitudinal Outcomes Study of the Subchondroplasty Procedure in the Foot/Ankle

Protocol #: KC.CR.I.AM.16.2 version 1

	
 1) Subject is pregnant at the time of surgery. 2) Subject is incarcerated. 3) Subject is involved in active litigation related to the condition being treated.
Pre-Operative Evaluations	
Initial study procedures include patient demographics, medical history, foot and ankle history, activity level, and each of the assessments and measures that will be applied longitudinally, including:
 
 • Use of pain medications • Subject-reported outcomes: 
 ○ EQ-5D ○ Foot Function Index (FFI) ○ Numeric Pain Scale
Study Procedure	Each subject will undergo a Subchondroplasty® Procedure in at least one of the bones in the foot and/or in the ankle joint.
Follow-Up	
 • A numeric pain scale will be collected at the first post-operative visit at approximately 2 weeks • Thereafter, subjects complete self-reported outcomes measures post-operatively at 6 weeks, 3 months, 6 months, 1 year and 2 years via telephone, internet or mail. • Study coordinator will contact the subject by telephone at the above time points to inquire about any revision surgeries and adverse events.
Telephone Interviews	
 • Study coordinator will contact subject by telephone at 3, 4 and 5 year time points to complete the numeric pain scale, global satisfaction survey and inquire about any revision surgeries.
Post-Operative Subject Questionnaires	
 • Use of pain medications • Subject-reported outcomes: 
 ○ EQ-5D ○ Foot Function Index (FFI) ○ Numeric Pain Scale ○ Subject Global Satisfaction Survey
Data Analysis	Data collected in this study will be summarized descriptively and will be the basis of study reports.

A Longitudinal Outcomes Study of the Subchondroplasty Procedure in the Foot/Ankle

Protocol #: KC.CR.I.AM.16.2 version 1

4.0 Abbreviations

AE	Adverse Event
BML	Bone Marrow Lesion
BMES	Bone Marrow Edema Syndrome
BSM	Bone Substitute Material
CaP	Calcium Phosphate
CFR	Code of Federal Regulations
CRF	Case Report Form
EDC	Electronic Data Capture
ePRO	Electronic Patient Reported Outcomes
FDA	Food and Drug Administration
FFI	Foot Function Index
HIPAA	Health Insurance Portability and Accountability Act
IFU	Instructions for Use
IRB	Institutional Review Board
MRI	Magnetic Resonance Image(ing)
NSAID	Non-steroidal Anti-inflammatory Drug
OA	Osteoarthritis
SAE	Serious Adverse Event
SCP	Subchondroplasty
TKA	Total Knee Arthroplasty
USADE	Unanticipated Serious Adverse Device Effect

5.0 Introduction

5.1 Clinical Background

Subchondral bone defects, sometimes called bone marrow lesions (BMLs), are MRI-visible defects that can be seen on fat-suppressed MRI sequences (T2FS, PDFS, etc.) where they appear as a hazy white area against the background of darker bone. Pathologists have shown that BMLs represent a healing response to trauma such as micro trabecular fractures of the subchondral bone [1]. BML defects have been highly correlated with pain symptoms in the knee [2, 3]; however, BMLs and their effect on foot/ankle pain and function have not been as thoroughly studied clinically. Moreover, because the ankle joint differs from other joints in the lower extremity with unique anatomic, biomechanical and biologic characteristics [4], so too do foot/ankle BMLs differ in prevalence, clinical presentation and clinical course [5].

Early articles in the radiographic literature are generally descriptive, characterizing the MR appearance of bone marrow lesions in the foot and ankle using a variety of pulse sequences. The etiology of these imaging features can sometimes be attributed to marrow abnormalities such as osteonecrosis, stress fracture, bone contusion, tumor, etc., [5, 6, 7, 8, 9] however not all bone marrow lesion patterns are as clear cut [5]. BMLs in the foot and ankle tend to involve multiple bones, are generally seen in younger patients and present with a clinical history of prolonged pain without a distinct history of prior trauma [5, 10, 11]. In a retrospective review of 72 patients whose MRIs of the foot demonstrated edema-like bone marrow abnormalities, Zanetti et al. concluded that edema-like patterns of unknown etiology are clinically relevant and predictors of long-lasting pain [10]. These findings were substantiated by Fernandez-Canton, et al. in a comparison of MRI imaging one year after the initial diagnosis of transient bone marrow edema syndrome (BMES) in 25 patients. Previously, BMES had been considered a benign disease that typically resolved in 3-12 months, but in this study, almost a third of the patients showed persistence of edema at one year with 8% showing no improvement, leading to the conclusion that patients experience pain for an extended period of time [8].

Treatment options for BMLs of the foot and/or ankle have been conservative in nature, including non-steroidal anti-inflammatory drugs, injections, calcium, physical therapy, extracorporeal shock therapy and activity modification [5, 8, 11]. Operative treatments can be joint sparing or joint destructive, however, considering the generally younger, physically active patient population with BMLs of the foot/ankle, a joint sparing procedure that does not preclude more extensive procedures in the future is desirable. Subchondroplasty[®] (SCP[®]) is a minimally-invasive procedure first described in 2007 to fill subchondral osseous defects associated with bone marrow lesions using an injectable bone substitute material (BSM), AccuFill[®] [12]. AccuFill is an injectable, self-setting, macro-porous, osteo-conductive, calcium phosphate bone graft substitute material that is intended for use to fill bony voids or gaps of the skeletal system of the extremities, spine (i.e. posterolateral spine), and the pelvis that are not intrinsic to the stability of the bony structure. These defects may be surgically created osseous defects or osseous defects created from traumatic injury to the bone. AccuFill is a bone graft substitute that resorbs and is replaced with new bone during the healing process. AccuFill has unique properties that allow it to flow through the osseous defects in trabecular bone and then set up hard at body temperature [13]. Two year results from a clinical study of the knee on 66 subjects considering total knee arthroplasty (TKA) has shown improvements in subject reported pain and function

with only 30% of subjects undergoing revision to TKA at 2 years [14]. The goal of this study is to track outcomes in a population undergoing SCP of the foot and/or ankle.

5.2 Product Description

The Subchondroplasty Procedure targets and fills bone defects with AccuFill BSM utilizing an arthroscopic / percutaneous approach as follows. Preoperatively, the BML bone defect is identified on fat-suppressed MRI, and the approach and trajectory is planned based on defect location. Using intraoperative fluoroscopy, the bone defect is localized relative to MRI findings. The appropriate AccuPort[®] Delivery Cannula is drilled to the bone defect. AccuFill BSM is then injected into the subchondral bone defect. The AccuFill fills the edematous void and hardens within the BML, and is resorbed over time and replaced with new bone during the healing process.

The Subchondroplasty procedure will be performed using two commercially available devices: AccuFill and SCP[®] Surgical Instrumentation.

AccuFill is an injectable, self-setting, macro-porous, osteo-conductive, calcium phosphate bone graft substitute material that is intended for use to fill bony voids or gaps of the skeletal system of the extremities, spine (i.e. posterolateral spine), and the pelvis that are not intrinsic to the stability of the bony structure. These defects may be surgically created osseous defects or osseous defects created from traumatic injury to the bone. AccuFill is a bone graft substitute that resorbs and is replaced with new bone during the healing process.

The SCP[®] Surgical Instrumentation is a set of manual surgical instruments used to target and deliver AccuFill to the osseous defect.

5.3 Preclinical Studies

Preclinical studies in established animal models were used to evaluate safety and effectiveness of AccuFill for treatment of a critical sized bone defect. A rabbit bilateral lateral femoral condyle defect model (4.8 mm diameter x 6 mm length cylindrical defect) through 24 weeks demonstrated that AccuFill caused bone induction and osteointegration at the implant sites, and was well tolerated.

No significant adverse events or indications of infections or rejections of the AccuFill material were observed in the preclinical evaluations of AccuFill. Studies demonstrated bone induction, osteointegration and potential for use as a bone void filler.

5.5 Regulatory Overview of Subchondroplasty

This study will evaluate the on-label use of AccuFill during the Subchondroplasty procedure.

The Subchondroplasty procedure will be performed using two commercially available devices. The regulatory status of each component of the system is described below:

1. AccuFill® Injectable Calcium Phosphate – Class II device; 510(k) Number K093447 - Calcium Salt Bone Void Filler Device, cleared by FDA. The package insert provides product description, indications, and usage information. (Appendix A).
2. SCP® Surgical Instrumentation – These are Class I manual surgical instruments. Per 21 CFR 888.4540, manual surgical instruments are premarket exempt.

6. Risk Analysis

This study was designed to assure that the benefits and knowledge gained by studying clinical outcomes associated with Subchondroplasty for treatment of BMLs in the foot/ankle outweigh the potential risks to the subjects. Alternative treatment options may require more invasive surgical therapy to treat the painful foot/ankle, up to and including arthrodesis or arthroplasty.

6.1 Risks of surgical intervention

With any surgical procedure, there are risks of complication including those risks currently associated with surgical interventions in the foot/ankle. These risks include intra-articular adhesions (scar tissue), superficial and/or deep wound infection, nausea and/or vomiting, bleeding, ankle pain, muscle weakness, and postoperative blood clot (hematoma). There are possibilities of wound re-opening, deep vein thrombosis (blood clot), pulmonary embolus (lung clot), vascular or nerve injury, and an allergic response to the anesthetic or medications. Some additional risks related to local anesthesia are swelling, pain, bleeding, bruising, nerve pain and loss of sensation in the skin and ligament around the foot/ankle.

6.2 Risks associated with subchondral implantation of AccuFill

Risks specific to the implantation of a bone marrow substitute may include tissue thinning over the implant site, tenderness/redness/edema, seroma/hematoma, infection, swelling/fluid collection and loss of contour. Migration, extrusion, dehiscence, fracture and sloughing of AccuFill can occur as a result of excessive trauma. Neurovascular injury may occur due to

surgical trauma. A pulmonary embolism may result from using this injectable bone void filler.

6.3 *Methods to minimize risk*

Only appropriate subjects, who meet the include inclusion and exclusion criteria, will be recruited into the study.

Study subjects will be monitored post-operatively to assess the surgical site for any acute and chronic adverse reactions to ensure proper medical treatment can be administered. Validated and standardized outcome scales and surveys will be used to collect subjects' data. Experienced orthopedic or foot/ankle surgeons will participate as investigators and have experienced staff to perform the study procedures.

6.4 *Benefits and Justification for the Study*

This is an observational study and there are no direct benefits to the subject, other than those associated with the treatment of a bone marrow lesion of the foot and/or ankle. The justification for this study is to learn more about patient outcomes following the Subchondroplasty procedure in the foot/ankle.

7.0 Study Objectives

The purpose of this post-market clinical study is to collect data on the short- and long-term outcomes for subjects who are undergoing or who have undergone the Subchondroplasty procedure in the foot and/or ankle in a standard clinical setting. Outcomes to be assessed include medication usage, pain, function, activity levels and patient satisfaction.

8.0 Study Design

This is a post-market, multicenter, prospective, patient outcomes centered study to evaluate the on-label use of AccuFill during the Subchondroplasty procedure. Enrolled subjects will satisfy the inclusion/exclusion criteria and have at least one BML in any of the bones of the foot and/or ankle joint.

Demographics, medical history and medications will be recorded at the time of enrollment. Subjects will complete validated patient reported outcomes measures pre-operatively. Surgical details including the SCP® procedure, concomitant surgical procedures and intraoperative safety events will be recorded. Pain outcomes will be assessed at the first post-operative visit (7-21 days). Information on medication usage, pain, function, health status and subject global satisfaction will be collected post-operatively at approximately 6 weeks, 3 months, 6 months, 1 year, and 2 years. Subject global satisfaction and numeric pain scores will be collected at 3 years, 4 years and 5 years post-surgery. Screening for adverse events and revision surgeries will occur throughout the study. The target enrollment is 250 subjects.

Subjects will complete the study at 5 years or will be withdrawn if the patient undergoes revision of the Subchondroplasty site. For the purposes of this protocol, a revision will be defined as any joint arthroplasty, fusion or any bone fixation, bone grafting or bone substitute procedure on the index foot/ankle.

9.0 Subject Selection Criteria

9.1 Inclusion Criteria

Candidates must meet ALL of the following:

- 1) Subject has at least one bone defect such as a BML, cyst or stress fracture confirmed by diagnostic imaging.
- 2) Surgeon considers the patient appropriate for the SCP procedure.
- 3) Subject provides voluntary signature on the IRB approved Informed Consent Form.
- 4) Subject is at least 18 years of age.
- 5) Subject must be physically and mentally willing and able, in the Investigator's opinion at the time of enrollment, to be compliant with the protocol and complete outcome forms via the internet, telephone or regular mail.

9.2 Exclusion Criteria

Candidates will be excluded if they meet ANY of the following:

- 1) Subject is pregnant at the time of surgery.
- 2) Subject is incarcerated.
- 3) Subject is involved in active litigation related to the condition being treated.

10.0 Study Procedures

10.1 Screening and Enrollment

Potential subjects will be screened from each investigator's patient population to determine if they meet the inclusion criteria described in Section 9.1 and none of the exclusion criteria described in Section 9.2. Subjects will not be invited to participate in the study until after approval of the protocol by the reviewing IRB. Subjects will be considered enrolled in the study if they meet the inclusion/exclusion criteria, sign a consent form, and undergo the SCP procedure. With prior approval of the Sponsor, the site may enroll subjects who have previously undergone Subchondroplasty. The subject will sign informed consent prior to completing follow-up study questionnaires. The Study Site will maintain a Subject Enrollment Log for all enrolled subjects.

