10.3 Preoperative Procedures

All preoperative procedures are to be completed prior to the study surgery. The Schedule of Events is listed in **Table 1**.

10.3.1 The preoperative visit will include collection of basic demographic information, medical history, foot and ankle history and current use of prescription and over-the-counter pain medication.

10.3.2 The subject is to complete a series of surveys and scales regarding their clinical outcomes at the time preceding surgery, including pain, stiffness, function, and activities. These scales include:

- The Foot Function Index (FFI)
- EQ-5D
- Numeric Pain Scale

10.3.3 For subjects enrolled after the completion of the Subchondroplasty procedure, basic demographic information, medical history, foot and ankle history and pre-op use of prescription and over-the-counter pain medication data should be collected, if available, from the subject's medical record. Pre-operative FFI, EQ-5D, and/or numeric pain scale should be entered if they were collected as part of the standard of care.

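### Already-operated patients may be enrolled with no limit on share or time since surgery, and the single overall summary does not separate them, which may understate revision and leaves them no guaranteed baseline

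*Combined protocol and SAP*

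**What the plan says.** **Enrolment.** Section 10.1 gives the default rule: "Subjects will be considered enrolled in the study if they meet the inclusion/exclusion criteria, sign a consent form, and undergo the SCP procedure". The next sentence adds an exception: "With prior approval of the Sponsor, the site may enroll subjects who have previously undergone Subchondroplasty". No cap, time window since surgery, consecutive-case rule or criterion for the sponsor's approval is given. On records, the section says: "The Study Site will maintain a Subject Enrollment Log for all enrolled subjects".

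**Design label.** Section 8.0 reads: "This is a post-market, multicenter, prospective, patient outcomes centered study to evaluate the on-label use of AccuFill during the Subchondroplasty procedure". It then states, with no exception: "Subjects will complete validated patient reported outcomes measures pre-operatively".

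**Population.** Section 7.0 covers "subjects who are undergoing or who have undergone the Subchondroplasty procedure in the foot and/or ankle in a standard clinical setting", and the synopsis does the same. Mixed enrolment is therefore disclosed.

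**Baseline of already-operated subjects.** Section 10.3.3 takes history and medication from the medical record where available. For the scales it says: "Pre-operative FFI, EQ-5D, and/or numeric pain scale should be entered if they were collected as part of the standard of care".

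**Revision.** Sections 8.0 and 11.1.2 take a subject out of the study when a revision occurs.

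**Analysis.** Section 14.0 plans a single overall descriptive summary of clinical performance, with Kaplan-Meier estimates and crude percentages. Strata are optional, and the examples are sex and body mass index. Enrolment type, delayed entry and missing baselines are not mentioned.

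**The concern.** A patient whose treated site has already been revised has little to offer a study that ends at revision. Patients who join after surgery are therefore likely to be those still unrevised, and their time from surgery to consent then contributes follow-up but no events. If that time is counted from surgery alongside subjects followed from the operation, the revision percentage is pulled down.

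Complications may be affected in the same way. Section 10.3.3 lists what to take from the record for these subjects, and adverse events between surgery and consent are not on the list. Outcome scores may also look better, because patients doing badly enough to be revised are under-represented.

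The baseline problem is separate. A post-operative mean would include everyone, while a change from baseline could include only those with a pre-operative score. The two summaries would then describe different groups.

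This matters because the study has one arm and no hypothesis test. The descriptive rates and means are its whole product, and Section 14.0 foresees their use in reports, presentations and publications.

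**Working it through.** **The plan's own figure.** The target of 250 subjects (Section 8.0) comes with no precision, event rate or dropout assumption, so there is nothing to reproduce. The plan also does not state the share of already-operated subjects or their lag from surgery to consent. What follows illustrates size under assumptions.

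**Revision: inputs**
- True 2-year revision rate p: 30% or 10%, both assumed. The only 2-year revision rate in the documents is the 30% in Section 5.1. It is revision to total knee arthroplasty in patients considering that operation, so it serves for scale only.
- Constant hazard h = -ln(1 - p)/2, which is 0.178 per year at p = 30%.
- Share f of already-operated subjects: 25% or 50%, assumed.
- Lag L from surgery to consent: 0.5, 1 or 1.5 years, assumed equal for all such subjects, all of them unrevised at consent.

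**Revision: formula.** With time counted from surgery and no delayed entry, the 2-year estimate is

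1 - [f·exp(-h(2 - L)) + (1 - f)·exp(-2h)].

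Example with p = 30%, f = 50%, L = 1: exp(-h) = √0.7 = 0.837 and exp(-2h) = 0.7. The estimate is 1 - (0.5 × 0.837 + 0.5 × 0.7) = 23.2%.

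| True rate | f | L = 0.5 y | L = 1 y | L = 1.5 y |
|---|---|---|---|---|
| 30% | 25% | 28.4% | 26.6% | 24.6% |
| 30% | 50% | 26.7% | 23.2% | 19.3% |
| 10% | 50% | 8.8% | 7.6% | 6.3% |

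**Comparison with sampling error.** The 95% half-width with 250 subjects is 1.96 × √(0.3 × 0.7/250) = 5.7 points at 30% and 1.96 × √(0.1 × 0.9/250) = 3.7 points at 10%.
- At 30% and f = 25%, the shortfalls are 1.6, 3.4 and 5.4 points, all inside the half-width.
- At 30% and f = 50%, they are 3.3, 6.8 and 10.7 points. The last two exceed it.
- At 10% and f = 50%, they are 1.2, 2.4 and 3.7 points. The last about equals it.

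**Does delayed entry repair it?** In a simulation of 400,000 subjects (p = 30%, f = 50%, L = 1 year), the estimate counted from surgery was 23.2%. With already-operated subjects entering the risk set at consent, it was 30.1%, against a true 30%.

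**Baseline.** Let b be the share of already-operated subjects with routine pre-operative scores (assumed 0 to 75%). The number with a baseline is 250 × [1 - f(1 - b)].
- f = 25%: 187.5 to 234.
- f = 50%: 125 to 219.

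The 95% half-width of a mean change is 1.96/√n in standard deviations of the change: 0.124 at n = 250 and 0.175 at n = 125.

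**The case against.** The strongest defence is that mixed enrolment is open. The synopsis and Sections 7.0 and 10.1 all state it, sponsor approval is needed, and Section 10.3.3 has a rule for these subjects' pre-operative data. The study is descriptive, Section 14.0 permits further strata, and revision is not among the outcomes named in Section 7.0. If few such patients are approved, or they consent soon after surgery, the effect is small or nil. All of this stands, and it limits the grade. It does not supply a cap, a planned split or a correction, and disclosure in Sections 7.0 and 10.1 does not reconcile Section 8.0 with them.

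Four stronger readings are tempting and are not supported:

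- *Every already-operated subject is known to be unrevised, and surgeons choose them on outcome.* No criterion bars a revised patient, and the exit rule concerns subjects already in the study. Section 10.1 speaks only of screening the investigator's patient population. Selection is a likely consequence, not a stated rule.
- *Pre-post change has no baseline.* Subjects consented before surgery have one, and Section 10.3.3 recovers some others. What is missing is a guarantee.
- *Outcome means are biased upwards.* A favourable shift lowers the mean on the numeric pain scale. The direction is towards better results, and it is possible rather than certain.
- *The plan commits to pooling and to a Kaplan-Meier revision curve.* Pooling is inferred from the single overall summary with no planned split. The Kaplan-Meier sentence does not name revision, although a crude percentage could be affected in the same way.

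**Conclusion.** The point holds as a gap between the enrolment rule and the rest of the plan. Section 10.1 admits already-operated patients without limit on share or time since surgery, Section 8.0 describes a prospective study with pre-operative measures, and Section 14.0 neither separates the two groups nor allows for late entry. Following the plan as written may understate revision and complications, may favour the outcome summaries, and leaves these subjects' baseline to routine care.

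The size cannot be fixed from the documents. Across the assumed 30% scenarios the shortfall runs from 1.6 to 10.7 points. It exceeds the sampling half-width only where half the cohort is already operated and the lag is a year or more. This rests on an assumed true rate, a constant hazard, a common lag, and already-operated subjects being unrevised at consent. A reader might infer that the study's revision rate is bound to be seriously wrong, but the documents do not support that. This should be fixed; it does not invalidate the study.

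**What to change.** - Record enrolment type (consent before or after surgery) and consent date for every subject. The date of surgery already reaches the sponsor under Section 16.1. The case report forms are not in the text available here, so the other two items may already be captured.
- Make subjects consented before surgery the main analysis set for rates and for change from baseline, and report already-operated subjects separately.
- Where revision is pooled, start already-operated subjects' risk time at consent (delayed entry). This corrects the time at risk. It does not correct any selection on how well unrevised patients are doing, so separate reporting is still needed.
- Limit change scores to subjects with a true pre-operative value and report how many lack one.
- Reword the design label and the pre-operative outcomes statement in Section 8.0 to agree with Sections 10.1 and 10.3.3.
- Optionally, ask sites that enrol after surgery for a de-identified count of patients treated in the period, if the IRB allows it. A patient-level log of everyone treated, with revision status, would run into the consent-first rule in Section 10.2 and the HIPAA terms in Section 16.1.

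The cost is analysis wording and, if not already captured, two data items. The main drawback is that the main analysis set may be smaller than 250. Enrolment after surgery need not stop.
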